15.5 Duration of Response and other Endpoint Definitions

The duration of overall response is measured from the time measurement criteria are met for CR or PR (whichever is first recorded) until the first date that recurrent or progressive disease is objectively documented (taking as reference for progressive disease the smallest measurements recorded since the treatment started), or death.

The duration of overall CR is measured from the time measurement criteria are first met for CR until the first date that recurrent disease is objectively documented, or death.

Stable disease is measured from the start of the treatment until the criteria for progression are met, taking as reference the smallest measurements recorded since the treatment started.

Rate of freedom from metastasis (FFM) is defined as the proportion of patients with documentation of progression of disease, during study participation, in whom no new lesions appeared.

In rare situations where PD or other endpoints could not be clearly assessed, the PI will review the records with the treating physician and provide a clinical judgment for purposes of endpoint documentation.

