High Dose Conditioning With Ifosfamide, Carboplatin, and Etoposide With Autologous Stem Cell Transplantation for Patients With Recurrent Nasopharyngeal Carcinoma

NCT02137096

03/23/2017

HIGH DOSE CONDITIONING WITH IFOSFAMIDE, CARBOPLATIN AND ETOPOSIDE WITH AUTOLOGOUS STEM CELL TRANSPLANTATION FOR PATIENTS WITH RECURRENT NASOPHARYNGEAL CARCINOMA

Investigator(s):

**[name]
[name]
[name]**

1. ABSTRACT / PURPOSE:

Nasopharyngeal carcinoma (NPC) is a rare disease in children and adolescents in the United States. There is no current standard treatment for recurrent disease. Treatment is individualized based on previous treatment (usually combined modality radiation and chemotherapy), sites of disease recurrence, and the patient's overall health status and anticipated tolerance of additional chemotherapy and radiotherapy. NPC is a highly chemosensitive disease, however, maintaining long-term remission is challenging. The role of consolidation with high dose chemotherapy has been investigated in number of pilot studies and shown to be tolerated. In this study, based on prior experience, the combination of high dose ifosfamide, carboplatin and etoposide followed by autologous stem cell rescue will be investigated as a consolidation therapy for locally advanced and metastatic NPC to increase disease remission rate and long term survival.

2. BACKGROUND:

Nasopharyngeal carcinoma (NPC) is a rare tumor in children accounting for approximately 1% of all childhood tumors, it also accounts for 20 – 50% of all primary nasopharyngeal tumors in this age group^{1,2}. It arises from the surface epithelial cells of the nasopharynx and has been associated with Epstein-Barr virus (EBV) infection². Most patients with childhood NPC have undifferentiated histology (WHO type III) and present with locoregionally advanced disease². Pediatric and adolescent patients are treated based on adult regimens with radiotherapy as the principal mode of treatment³. The addition of chemotherapy has been shown to improve survival in patients with locally advanced NPC⁴. Despite standard combined modality therapy, 20 – 30% of patients with NPC will present with recurrent or metastatic disease⁴. Most recurrences occur within the first two years of diagnosis and repeat radiation therapy is often not an option. Various combinations of chemotherapy have been tried in adults and in children with varying results, but overall response and survival have remained dismal.

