10. EFFICACY ASSESSMENTS

- 10.1.** Tumor response will be assessed using MRI/CT/PET imaging of the primary site and known metastatic sites.
- 10.2.** Measureable disease: the presence of at least one measurable lesion that can be accurately measured in at least one dimension (the longest diameter) and with a minimum size of 10 mm by CT or MRI scan.
- 10.3.** Non-measurable lesions: all other lesions including leptomeningeal disease, pleural/pericardial effusion, and blastic bone lesions.
- 10.4.** All measurements should be recorded in metric notation, using a ruler or calipers using the same method of assessment to characterize each identified and reported lesion at baseline and during follow-up.
- 10.5.** All baseline evaluation should be performed as close as possible to the initiation of conditioning treatment and not more than 30 days before conditioning treatment begins.
- 10.6.** Response Criteria include:

11. Response Criteria for Patients with Solid Tumors

This study will use a modified version of the Response Evaluation Criteria in Solid tumor (RECIST) from the NCI to evaluate disease response. The modifications will include volumetric measurement of the primary NPC and assessment of associated adenopathy. Measurable and non-measurable metastatic foci in the lungs, bones and liver will be evaluated as per RECIST.

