15.1 Sample Size Determination

This is a pilot study and due to the limited number of potential patients who may present with this rare disease, a sample size of 10 patients was chosen based on availability.

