15.3 Analysis of Secondary Endpoints

The objective RR is equal to the proportion of patients achieving a best overall response of partial or complete response (CR + PR), according to imaging from the start of the treatment until disease progression/recurrence. Clinical benefit rate is equal to the objective RR plus the proportion of patients attaining stable disease (CR + PR + SD). Patients who do not have a tumor response assessment for any reason will be considered nonresponders and will be included in the denominator when calculating the response rate. The number of patients achieving a response will be divided by the total of patients treated to yield the proportion responding. Exact confidence bounds (95% CI) will be calculated.

Overall survival is defined as the time from the date of treatment start to the date of death from any cause. If the patient is alive at the end of the follow-up period or is lost to follow-up, OS will be censored on the last date the patient is known to be alive. OS will be evaluated by the Kaplan-Meier method and a 2-sided 95% CI will be provided for the median OS.

Time to progression (TTP) for responders only is measured from the time measurement criteria are first met for CR/PR (whichever is first recorded) until the first date that the criteria for PD are met, or death. TTP will be

estimated with the Kaplan-Meier method; a 90% CI will be provided for the median TTP. Patients who do not relapse are censored at the day of their last objective tumor assessment. The freedom from metastasis rate is defined below and will be calculated based on an intention to treat principle. Determination of the anatomic site of first failure for patients with PD will be recorded and analyzed. Duration of response is also defined below.

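### Freedom from metastasis is scored by absence of new lesions regardless of site, so it miscounts new local lesions and, unless only new metastases are meant, growth of existing ones

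*Combined protocol and SAP*

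**What the plan says.** FFM is a secondary endpoint. Section 15.5 defines it as "the proportion of patients with documentation of progression of disease, during study participation, in whom no new lesions appeared". No anatomic site is named there, and nothing elsewhere limits new lesions to distant ones. Section 15.3 adds only this: "The freedom from metastasis rate is defined below and will be calculated based on an intention to treat principle". As a separate item, 15.3 states: "Determination of the anatomic site of first failure for patients with PD will be recorded and analyzed". The FFM definition does not use that item.

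Section 11 separates the disease compartments. For local and nodal disease: "The modifications will include volumetric measurement of the primary NPC and assessment of associated adenopathy". For distant disease: "Measurable and non-measurable metastatic foci in the lungs, bones and liver will be evaluated as per RECIST".

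Distant metastases at entry are foreseen. Section 1 describes the regimen as a "consolidation therapy for locally advanced and metastatic NPC", and section 10.1 says "Tumor response will be assessed using MRI/CT/PET imaging of the primary site and known metastatic sites". Neither the inclusion nor the exclusion criteria (5.5.1, 5.5.2) mention metastases, so such patients are admitted but their expected share is not given. On size, 15.1 says "a sample size of 10 patients was chosen based on availability".

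**The concern.** Whether a lesion is new and whether it is a metastasis are different questions. A recurrence in the nasopharynx can be a new lesion without being a metastasis, and a lung metastasis present at baseline can progress without any new lesion. The definition answers the first question under a name that promises an answer to the second.

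Two kinds of progressor are affected, and they push the rate in opposite directions. What is at stake is how one reported secondary rate can be read: a published FFM figure could include patients whose metastases progressed and leave out patients whose disease never left the nasopharynx or neck.

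**Working it through.** The plan states no FFM rate, assumed progression count or share of patients with baseline metastases, so there is no figure of its own to reproduce. The check applies the definition to each single route to progression and compares it with two readings of the name.

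**Step 1: classification.**

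| Only form of progression | Count | 15.5 as written | By site (any distant progression fails) | Freedom from new distant metastasis |
|---|---|---|---|---|
| Existing distant lesion grows, nothing new | a | free | not free | free |
| New local lesion (or new regional node, if nodes are not metastasis) | b | not free | free | free |
| Primary or existing nodes grow | c | free | free | free |
| New distant lesion | d | not free | not free | not free |

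The written rule departs from the site-based rule in rows a and b only. It departs from the new-distant-metastasis reading in row b only.

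**Step 2: formulas.** Let k = a + b + c + d be the number of progressors.

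- As written: (a + c)/k.
- By site: (b + c)/k. As written minus by site: (a − b)/k.
- New distant only: (a + b + c)/k. As written minus new distant only: −b/k.

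Each net misclassified patient therefore moves the rate by 1/k: 1/6 = 16.7 percentage points at k = 6 and 1/10 = 10 points at k = 10.

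**Step 3: illustration.** The counts are assumptions: 6 of the 10 patients progress, each by one route. Intervals are exact (Clopper-Pearson) 95%.

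| a, b, c, d | As written | By site | Difference | New distant only |
|---|---|---|---|---|
| 2, 0, 2, 2 | 4/6 = 66.7% (22.3 to 95.7) | 2/6 = 33.3% (4.3 to 77.7) | +33.3 points | 4/6 = 66.7% |
| 0, 2, 2, 2 | 2/6 = 33.3% (4.3 to 77.7) | 4/6 = 66.7% (22.3 to 95.7) | −33.3 points | 4/6 = 66.7% |
| 1, 1, 2, 2 | 3/6 = 50% (11.8 to 88.2) | 3/6 = 50% (11.8 to 88.2) | 0 | 4/6 = 66.7% |

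In the third row the two rates agree although two patients are classified wrongly. Against the new-distant-metastasis reading, the written rule can only be too low.

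**Step 4: denominator.** Section 15.5 can be read as confining the rate to progressors, which does not fit the intention-to-treat statement in 15.3. Over all 10 treated patients, with the 4 non-progressors counted as free, the three rows become 8/10 against 6/10, 6/10 against 8/10, and 7/10 against 7/10. Changing the denominator shrinks the effect per patient to 10 points but does not remove the misclassification.

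**Step 5: does anything else in the plan correct it?** The site of first failure is analyzed on its own and does not enter FFM. The closing sentence of 15.5 brings in the PI's judgment only where an endpoint cannot be clearly assessed. A plainly growing lung metastasis, or a plain new nasopharyngeal lesion, is not such a case.

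**The case against.** The strongest reply is that 15.5 states an open operational rule. In a population that may enter with metastases, it can be read as freedom from new metastasis, and growth of an old lung lesion is then rightly not a failure. That stands as a possible intention. It reduces the existing-metastasis half to a naming problem, but does not explain why a new local lesion is scored as metastasis.

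Second, no section defines metastasis as distant only; section 11 sets measurement methods, not the meaning of FFM. That also stands in part. If regional nodes were meant to count, the new-node example falls away, and the firm case is a new non-nodal local lesion.

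Third, impact is limited. There is no hypothesis or decision rule on FFM, the exact intervals at k = 6 overlap widely, every patient concerned is a PFS event in any case, and the site of first failure is reported alongside. All of this is right.

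A reader might infer something stronger: that a regimen failing only in existing distant sites would be reported as 100% free from metastasis when the truth is 0%. The arithmetic permits it (a = k), but the documents do not support it as a finding. They give no counts and no share of patients with baseline metastases, and the 0% is the truth only if a site-based endpoint was intended. A reader might also infer that FFM is biased upward; the second row of the illustration shows the opposite is equally possible.

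**Conclusion.** The definition is wrong as written, within limits. A new local lesion scored as metastatic failure fits neither reading of the name. Growth of existing distant metastases scored as freedom from metastasis is acceptable only if new metastasis was meant, which neither the name nor the text says.

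The size is 1/k per net misclassified patient, in either direction under a site-based reading, with cancellation possible. How many patients would be affected cannot be derived from the documents. The conclusion assumes that section 11 reflects how the protocol uses the word metastatic, and that the definition would be applied literally. It concerns one descriptive secondary endpoint in a 10-patient pilot. PFS, response rate and OS do not use the FFM rule and are unaffected.

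**What to change.** Amend 15.5 as follows.

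- Define distant failure by site: any new or progressing lesion outside the nasopharynx and regional nodes, at any time during study participation. State explicitly how regional nodes are classed.
- Do not rely on the site of first failure alone. A patient with local first failure and later distant spread would be scored free, while 15.5 covers the whole of study participation and 5.4 allows follow-up to 5 years.
- Calculate FFM over all treated patients, to agree with 15.3, and state how patients without documented progression are counted.
- Show results separately for patients with and without distant metastases at baseline. For those with baseline metastases, report progression by site (local, regional, existing distant, new distant), and label any rate based only on new lesions as freedom from new distant metastasis.

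The CT or MRI and PET already scheduled in section 8 (baseline, day 100, 6 and 9 months, 1 year, then yearly to 5 years) can supply the data. The cost is a protocol wording amendment with IRB approval under 16.1, recording the site of later failures as well as the first, and small subgroups within a sample of 10.

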15. STATISTICAL CONSIDERATIONS

Statistical analyses will be conducted by the study biostatistician using SAS v9.1 (SAS Institute, Cary, NC).

Routine data listing or tabulation review during the study conduct will be performed to identify missing data, anomalies, outliers, etc. Missing data will generally not be imputed. Baseline is defined as the last non-missing measurement for a variable prior to the initial dose of any investigational product.

Descriptive statistics will be provided to summarize demographic and baseline characteristic parameters. Categorical data will be summarized as frequency and its corresponding percentage. For continuous data, frequency (n), mean, standard deviation, median (as appropriate), minimum, and maximum will be provided for each parameter.

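### Freedom from metastasis is labelled intention to treat but defined among progressors, so fewer progressions without new lesions can lower the rate

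*Combined protocol and SAP*

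**What the plan says.** Section 15.3 lists the rate among the secondary endpoints: "The freedom from metastasis rate is defined below and will be calculated based on an intention to treat principle". Section 15.5 then gives its only definition, the "proportion of patients with documentation of progression of disease, during study participation, in whom no new lesions appeared". No time point is set. Under section 5.4, follow-up can last up to 5 years after transplant.

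The response rate, also in section 15.3, is handled differently. Its denominator is explicit: "The number of patients achieving a response will be divided by the total of patients treated to yield the proportion responding". Unassessed patients are covered too: "Patients who do not have a tumor response assessment for any reason will be considered nonresponders and will be included in the denominator".

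Three other provisions come near the point without settling it:

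- Section 15: "Missing data will generally not be imputed".
- Section 15.5, which provides for clinical judgment by the investigator: "In rare situations where PD or other endpoints could not be clearly assessed, the PI will review the records with the treating physician".
- Section 15.3, on where disease first fails: "Determination of the anatomic site of first failure for patients with PD will be recorded and analyzed".

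**The concern.** An intention-to-treat rate keeps every patient in the denominator. The definition in section 15.5 selects patients by something that happens after treatment, namely documented progression. A patient who stays in remission and never develops a metastasis is the clearest case of freedom from metastasis, yet does not count as one.

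The name does not fit either. The definition turns on whether a lesion is new, not on where it is. Growth of an existing metastasis counts as free, and a new locoregional lesion counts against. Section 1 says the study covers metastatic as well as locally advanced disease, so both situations can arise.

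What is at stake is how one descriptive figure is read. A low rate could mean many new lesions, or merely few progressions without them. The second would be a good result reported as a poor one.

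**Working it through.** **Inputs.** N = 10 (section 5.2; section 15.1 says the number was chosen on availability). The plan gives no expected rate, no expected number of progressions and no interval for this endpoint, so there is no planned figure to reproduce. All patient counts below are assumed. The intervals are exact (Clopper-Pearson) 95%, borrowed from the response rate.

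**Notation.** L = progressors without new lesions, M = progressors with new lesions, P = L + M.

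- Literal reading of section 15.5: L/P.
- Same words with all patients as the denominator: L/N.
- Free of new lesions among all treated, if all are alive and scanned: (N − M)/N.

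**Size, with M = 2.**

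| P | L | L/P | L/N | (N − M)/N | All treated minus literal |
|---|---|---|---|---|---|
| 10 | 8 | 80.0% | 80% | 80% | 0 points |
| 8 | 6 | 75.0% | 60% | 80% | 5.0 points |
| 6 | 4 | 66.7% | 40% | 80% | 13.3 points |
| 4 | 2 | 50.0% | 20% | 80% | 30.0 points |

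The intervals are 22.3 to 95.7% for 4/6, 6.8 to 93.2% for 2/4 and 44.4 to 97.5% for 8/10.

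The last column follows a general rule. Since L = P − M,

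(N − M)/N − L/P = M/P − M/N = (M/P) × (N − P)/N.

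The gap is the share of progressors with new lesions times the share of patients who have not progressed. For P = 6 it is (2/6) × (4/10) = 0.133.

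**Direction.** Move one patient from progressed without new lesions to not progressed, with M fixed. The literal rate changes from L/(L + M) to (L − 1)/(L + M − 1), a fall of M/[(L + M)(L + M − 1)]. This is positive whenever M is at least 1. Of the 55 such one-patient moves possible with N = 10, the rate falls in all 45 with M ≥ 1. With M = 0 it stays at 100% in 9 and becomes 0/0 in 1.

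Under L/N, every such move lowers the rate by 1/10. A trial with no progressions at all would score 0/10.

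**Deaths and missing scans.** Suppose 3 patients progress without new lesions, 2 progress with them, 2 die without documented progression, 1 is never scanned and 2 remain progression-free.

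- As written: 3/5 = 60% (14.7 to 94.7%).
- Alive, scanned and free of new lesions, taking the 3 progressors without new lesions as alive: (3 + 2)/10 = 50% (18.7 to 81.3%).
- If the 2 deaths and the unscanned patient counted as free instead: (10 − 2)/10 = 80%.

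The literal rate can therefore lie above or below an all-treated rate, depending on a rule the plan does not state.

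**The case against.** The strongest reply is that the wording is ambiguous rather than wrong. It can be parsed as progressors without new lesions over all patients, which fits the intention-to-treat sentence. That is a fair reading, but it does not rescue the endpoint: non-progressors enter the denominator only to be counted as not free, and the rate still moves the wrong way.

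A second reply is that the effect is probably small. Section 5.5.1 requires at least a second recurrence or progression, so many patients may progress again, and the gap from the literal rate is then 0 to 5 points (P = 10 or 8, M = 2). With 10 patients the intervals overlap almost completely. This stands as a limit on size. But the documents do not predict the number of progressions, and for a given share of progressors with new lesions the gap is widest when fewest patients progress.

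Third, the deaths example compares the literal rate with a composite that includes survival, so the reversal comes partly from that choice. This is correct. The example shows only that the handling of deaths has to be stated.

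Fourth, the site-of-first-failure analysis already separates local from distant failure. It helps, but it covers only patients with progression and only the first failure, and it leaves the denominator unchanged. The missing-data sentence and the investigator-judgment provision set no denominator either.

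**Conclusion.** The concern holds. Sections 15.3 and 15.5 do not agree on the literal reading, and neither reading of the definition measures freedom from metastasis in all patients. The direction of the error follows from the definition, given at least one progressor with new lesions for the literal reading and without that condition for the other.

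The size is not known. With 2 new-lesion progressors among 10 patients, all alive and scanned, the literal rate understates the all-treated rate by 0 to 30 points as the number progressing goes from 10 down to 4.

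The consequence is limited. This is a single-arm pilot, the rate carries no hypothesis, and it is not among the specific aims in section 3. It should be corrected, at the low end of priority.

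**What to change.** Define the rate over all treated patients, as for the response rate, and rename it freedom from new lesions. State that all treated is what intention to treat means here: section 5.5.4.1.4 excludes patients whose stem cell collection is inadequate, and others may drop out before conditioning. Then choose one form:

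- **(a)** The proportion alive and free of new lesions at a named scheduled imaging visit, with an exact 95% CI. Deaths and patients without a scan at that visit count as not free, and the result is described as a composite with survival.
- **(b)** The cumulative incidence of a first new lesion from treatment start, with death without a new lesion as a competing event and censoring at the last scan. Use the Aalen-Johansen estimate with a log(−log) 95% CI at a named time point.

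With 10 patients, (a) is simpler and its interval is exact; the interval in (b) is approximate and would rest on very few events. Under either form, say whether new lesions appearing after a first progression without new lesions count. Keep the site-of-first-failure analysis alongside.

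The cost is an amendment to section 15 with written IRB/IEC approval (section 16.1). No scans are added to the section 8 schedule, which has CT/MRI and PET at Day 100, 6 and 9 months, 1 year and yearly to 5 years. Two clarifications are needed. Section 10.1 reads "Tumor response will be assessed using MRI/CT/PET imaging of the primary site and known metastatic sites", so the amendment should say that scheduled scans are also read for new sites. The schedule does not say whether imaging continues after progression, which has to be settled if later new lesions count; recording them may need one instruction. The sponsor should expect that the rate may look less favourable once deaths and missing scans count against it.
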